6.3. Statistical analysis

Primary hypotheses:

Statistical analyses for the two primary hypotheses will follow the intention-to-treat paradigm, which means that all randomized patients with baseline and 96 week liver biopsies will be included in the treatment group to which they were assigned. Any randomized patient who does not have the requisite biopsies will be accounted for and compared by assigned treatment group. Patients not able

to be included in the intention-to-treat analyses will be compared to those who are included with respect to demographic and other characteristics.

Since the primary outcome measure, defined in Section 6.2, is a binary indicator of improvement in histologic activity score after 96 weeks of treatment compared to baseline and since the randomization is stratified by clinic, P-values will be derived from the Mantel-Haenszel χ^2 test for stratified 2x2 tables (66). Two P-values will be derived: one comparing proportions improved in the group assigned to pioglitazone compared to the group assigned to placebo and another comparing the group assigned to vitamin E to the group assigned to placebo. Since two primary comparisons are planned, a P-value of 0.025 will be considered significant, applying a Bonferroni correction for multiple comparisons.

Given the randomized design and adequate size planned for the PIVENS trial, it is unlikely that confounding of the treatment groups by covariates related to the change in histologic activity score will occur. However, if confounding should occur, logistic regression analyses with histologic improvement as the binary response and treatment group indicator and any suspected confounders as covariates will be carried out to determine the sensitivity of the primary P-value to confounding.

Secondary hypotheses:

The first secondary hypothesis, that pioglitazone and vitamin E are equally effective in achieving histologic improvement, involves the primary outcome measure. Equivalence will be assessed in two ways: (1) a formal test for equivalence, testing that the difference between proportions improved in the pioglitazone and vitamin E groups does not exceed 10% and (2) 95% confidence intervals on the difference in proportions improved.

In general, analyses for outcomes related to other secondary hypotheses will be conducted in two ways. Improvement will be analyzed both as a binary outcome (improved vs. not improved) and also in terms of the numerical change in the outcome. Binary outcomes will be compared using the uncorrected χ^2 test for 2x2 table. Numerical changes will be analyzed by descriptively comparing the between-treatment group differences in mean and median changes; P-values will be derived from Wilcoxon rank sum tests for comparison of the distribution of changes in each group. If concerns about confounding arise, logistic regression models for improvement outcomes and linear regression models for numerical change outcomes will be used to correct for the confounding. Analyses for secondary hypotheses will generally involve three separate analyses, one for each treatment group comparison: pioglitazone vs. placebo, vitamin E vs. placebo, and pioglitazone vs. vitamin E. No adjustments for multiple comparisons will be applied to the secondary hypotheses; however, any significant findings must be interpreted taking into account the strength of the finding and its biologic plausibility.

Other questions to be addressed:

A series of other questions of interest were listed in Section 6.1. Analyses related to these questions will involve a mix of appropriate exploratory and confirmatory analyses, similar, but not limited to those described for the primary and secondary hypotheses.

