6.4. Missing data

The occurrence of missing data in this trial is expected to be low and, when present, is expected to be equally distributed across the 3 treatment groups. We estimate that careful selection of patients during the 6 months screening phase and the consent process should result in no more than 10% missing data from patients who drop out before completing the 96 week treatment period. In primary, intention-to-treat analyses, patients with missing data will be considered unimproved on the primary outcome measure.

The proportions with missing data will be compared across treatment groups using χ^2 tests. Nonsignificant P-values indicate that the data are missing at random (MAR). If this is the case, analyses of the non-missing data are not threatened. If the amount of missing data exceeds 10% and the data are MAR, then a variety of sensitivity analyses will be carried out to compare to the primary analysis using all available non-missing data: (1) compare pessimistic and optimistic imputations of the missing values, (2) correct for missing data using multiple imputation with 10 replicated samples, and (3) use mixed random effects logistic or linear regression models, depending on the type of outcome measure. Although unlikely in a large trial, it is possible that the missing data are not MAR and the missing data are non-ignorable. A few statistical methods are available when there are non-ignorable missing data and these would be employed; however; all such methods involve strong assumptions that cannot be verified from the available data.

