6.5. Justification of sample size

The planned sample size for the PIVENS trial is 240 patients with equal allocation to each of the three treatment groups (80 per group).

We based the sample size estimates on a two-group, binomial comparison of the proportions of patients satisfying the primary outcome, improvement in the histologic activity score (defined in Section 6.2) over the course of treatment. Since PIVENS is a three group trial with two primary hypotheses, we assume that the two primary comparisons, pioglitazone vs. placebo and vitamin E vs. placebo, require the same sample size and reduce the type I error from 0.05 to 0.025 (Bonferroni correction). Expected proportions improved were approximated using pilot data from a 48-week pioglitazone study ([name] and [name], personal communication) and from the placebo group in a two-year randomized trial of Urso vs. placebo ([name], personal communication). Currently, there are no available data to estimate the response in vitamin E, which is assumed, for purposes of planning the trial, to be the same as for pioglitazone.

41

The sample calculations were performed using the nQuery Advisor 5.0 (67) software using the formula:

$$n = \frac{\left[z_{1-\alpha/2}\sqrt{2\overline{\pi}(1-\overline{\pi})} + z_{1-\beta}\sqrt{\pi_1(1-\pi_1) + \pi_2(1-\pi_2)}\right]^2}{(\pi_1 - \pi_2)^2}$$

where,

- n = sample size per group
- π_1 = expected proportion improved in placebo group (assumed=0.14)
- π_2 = expected proportion improved in pioglitazone or vitamin E group (0.40)
- $\overline{\boldsymbol{\pi}}$ = average of π_1 and π_2
- α = Two-sided type I error (0.025, Bonferroni corrected for two comparisons)
- β = Type II error (0.10; i.e., 90% power)

The number per group, using the above formula is 71. Inflating this number by the 10% expected missing data rate yields approximately 80 patients per group, or a total of 240 for the trial.

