6.6. Interim analysis

An independent Data and Safety Monitoring Board (DSMB), appointed by the NIDDK, is responsible for approving the protocol for the PIVENS trial and for monitoring the accumulated interim data as the trial progresses to ensure patient safety and to review efficacy. The DSMB is a multidisciplinary group with a written charge provided by the NIDDK. The DSMB reports to the NIDDK, which will, in turn, communicate DSMB recommendations to the investigators, as appropriate. The DSMB meets in person to approve the protocol. After the trial commences, the DSMB meets twice a year to review data or other issues – once in person and once by telephone conference. The DSMB may request more frequent meetings if necessary to fulfill its charge. It may also request additional safety reports on a more frequent basis. For example, all serious adverse events are reported to the DSMB for their consideration and recommendations as they occur.

Interim data on safety measures requested by the DSMB are reviewed at each of the scheduled semi-annual full meetings. Two additional written safety reports will be reviewed by the DSMB between scheduled full meetings. Serious adverse events will be reviewed by the DSMB as they occur with the option of a teleconference discussion if any DSMB member so requests.

The DSMB will review quarterly reports by masked treatment groups of incident hepatotoxicities, as well as counts of patients who required more frequent liver function testing due to

42

rises in ALT levels of more than 1.5 times baseline ALT or beyond 250 U/L. The DSMB will also examine the trends in ALT or AST levels for each patient who experiences a rise in ALT.

The DSMB reviews one planned interim analysis of the primary outcome measure. O'Brien-Fleming statistical stopping guidelines for efficacy apply. This interim efficacy analysis will occur when approximately 50% of the data are complete or when approximately 120 of the 240 patients have completed baseline and 96 week biopsies.

The DSMB also reviews the overall progress of the trial in terms of recruitment and data quality and makes a formal recommendation to the NIDDK at the end of each scheduled meeting as to whether the trial should continue unmodified, continue with protocol modifications, or be stopped.

7. Human subjects issues

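### Sections 6.3 and 6.4 give two different rules for patients without a week-96 biopsy in the primary analysis, and the protocol does not say which governs

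*Protocol*

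**What the plan says.** Section 6.3 says the primary hypotheses are analysed by intention to treat and then explains the term: "all randomized patients with baseline and 96 week liver biopsies will be included in the treatment group to which they were assigned". Randomized patients without the required biopsies are accounted for by arm, and those not able "to be included in the intention-to-treat analyses will be compared to those who are included with respect to demographic and other characteristics". The significance rule for each of the two comparisons is that "a P-value of 0.025 will be considered significant, applying a Bonferroni correction for multiple comparisons".

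The first paragraph of Section 6.4 expects no more than 10% missing data, spread equally over the three arms, and then says: "In primary, intention-to-treat analyses, patients with missing data will be considered unimproved on the primary outcome measure". The second paragraph says that if missing data exceed 10% and are missing at random, "a variety of sensitivity analyses will be carried out to compare to the primary analysis using all available non-missing data". Its list includes pessimistic and optimistic imputation, multiple imputation and mixed models.

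Section 6.5 computes 71 per group and inflates to about 80 for 10% missing data. Section 6.6 plans one interim efficacy analysis at about half the data, or when "approximately 120 of the 240 patients have completed baseline and 96 week biopsies".

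**The concern.** The two sections cannot both describe the primary analysis. Under 6.3 the denominator in each arm is the patients with two biopsies. Under 6.4 it is everyone randomized to the arm. Reading 6.4 as merely completing 6.3 does not work, because 6.3 says outright that some patients are not in the intention-to-treat analyses.

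Both rules carry the labels primary and intention-to-treat, so either could be defended after the data are seen, separately for each active arm. The rule in 6.3 also selects patients on an event after randomization (having the week-96 biopsy) while keeping the intention-to-treat name. This is not a detail left to a statistical analysis plan: the protocol fixes the rule twice, in different ways.

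**Working it through.** **Inputs.** From Section 6.5: placebo proportion 0.14, active proportion 0.40, two-sided alpha 0.025 per comparison, 90% power, 80 per group. From Section 6.4: 10% missing. Assumed, because the documents give no such data: the example counts, how missing biopsies split between arms, missing rates of 15% and 20%, outcomes independent of missingness, and one unstratified table in place of the clinic-stratified Mantel-Haenszel test.

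**1. The plan's own figure.** In the 6.5 formula, z(0.9875)=2.241, z(0.90)=1.282 and the average proportion is 0.27. This gives n=70.1, rounded up to 71. Then 71/0.9=78.9, which agrees with about 80. This inflation treats missing patients as lost from the denominator and leaves 0.14 and 0.40 undiluted, as the 6.3 rule would.

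**2. Power under each rule, equal missing fraction m.** Solving the 6.5 formula for power:

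power = Φ( [ |π₂−π₁|·√n − 2.241·√(2π̄(1−π̄)) ] / √(π₁(1−π₁)+π₂(1−π₂)) )

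Under 6.3, n=80(1−m) with 0.14 vs 0.40. Under 6.4, n=80 with 0.14(1−m) vs 0.40(1−m).

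| Missing | 6.3: n per arm | 6.3: power | 6.4: proportions (n=80) | 6.4: power |
|---|---|---|---|---|
| 10% | 72 | 90.8% | 0.126 vs 0.36 | 89.6% |
| 15% | 68 | 89.0% | 0.119 vs 0.34 | 86.9% |
| 20% | 64 | 86.9% | 0.112 vs 0.32 | 83.8% |

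The cost of choosing missing = unimproved is 1.2, 2.1 and 3.1 percentage points. At 0.126 vs 0.36, 90% power needs 82 per group (81.1 rounded up).

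**3. Same patients, two rules.** Uncorrected χ² = N(ad−bc)²/(product of the four margins), with 80 randomized per arm and 16 of 160 (10%) missing in total. Active arm first.

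- 10 active and 6 placebo missing, 24 and 13 improved. Completers, 24/70 vs 13/74: χ²=144·866²/(70·74·37·107)=5.27, P=0.022, significant. All randomized, 24/80 vs 13/80: χ²=160·880²/(80·80·37·123)=4.25, P=0.039, not significant.
- 4 active and 12 placebo missing, 25 and 12 improved. Completers, 25/76 vs 12/68: χ²=144·788²/(76·68·37·107)=4.37, P=0.037, not significant. All randomized, 25/80 vs 12/80: χ²=160·1040²/(80·80·37·123)=5.94, P=0.015, significant.
- 8 and 8 missing, 24 and 13 improved. Completers, 24/72 vs 13/72: χ²=144·792²/(72·72·37·107)=4.40, P=0.036. All randomized: P=0.039 as above. Neither is significant, so the verdicts agree.

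**4. How often the verdicts differ.** Simulation with 200,000 trials per scenario at 0.40 vs 0.14 gave opposite verdicts in 2.7% of trials with 10% missing in each arm, 9.9% with 15% active and 5% placebo missing, and 4.5% with 5% active and 15% placebo missing.

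**The case against.** Section 6.4 is the section on missing data and states its rule plainly, so one may argue that the specific sentence governs the general one in 6.3. That is a sensible guide to the intent and the reason to align 6.3 to 6.4. But the protocol never says so, and 6.3 describes excluded patients explicitly, so the contradiction stands.

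The protocol's own expectation is equal missingness, and there the rules nearly agree. That also stands. The reversal in the 24-versus-13 example comes from the assumed 10/6 split and disappears at 8/8.

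Several supporting points are weaker than they look:

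- The 6.4 phrase on non-missing data is ambiguous. It may describe the primary analysis or the sensitivity analyses set against it. It can be read as a completer primary analysis but does not prove one.
- A reader might infer from 6.6 that dropouts are absent from the interim analysis. That text sets timing and does not define an analysis set.
- The inflation in 6.5 is a rough allowance. It fits 6.3 but does not define who is analysed.
- A reader might infer that stopping study drug removes a patient under 6.3. It does not. Section 5.8.1.4 keeps such patients in follow-up, and Section 5.8.1.1 follows those stopped for hepatotoxicity and offers them a biopsy. Only the missing biopsy excludes.

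**Conclusion.** The contradiction between 6.3 and 6.4 is real, lies in the protocol's own text, and needs correcting because it decides who enters the primary P-value. Its size depends on the balance of missing biopsies. With equal missingness at the expected 10%, it costs about one point of power and changes few verdicts. With unequal missingness it can change the verdict either way. These sizes rest on the assumptions listed with the calculation, above all the assumed splits.

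Two stronger readings are not supported. First, this is not mainly a loss of power: completers also lose power as missingness rises, to 89.0% and 86.9%, so the falls to 86.9% and 83.8% under the other rule cannot be charged to that rule alone. Second, missing = unimproved is not free of bias. When placebo patients drop out more, it favours the active arm, as the 4-versus-12 example shows. Choosing it removes the ambiguity, not the effect of unequal dropout.

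**What to change.** - **6.3:** Replace the definition based on having both biopsies with a statement that all randomized patients are analysed in their assigned arm and that a patient without an evaluable week-96 biopsy is counted as unimproved, in line with 6.4. Remove the reference to patients who cannot be included.
- **6.4:** Delete or reword the phrase on non-missing data so that it cannot be read as a second definition of the primary analysis. Name the completer analysis and multiple imputation as sensitivity analyses, because the primary rule can itself be biased when dropout is unequal.
- **6.5:** Restate power as about 89.6% with 80 per group at 10% missing.
- **6.6:** State that the interim efficacy analysis uses the same missing-data rule.

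The cost is a wording change before unmasking and a stated power slightly below 90%. No added patients or procedures are needed; keeping a full 90% would take 82 per group.

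### Holm's step-down would keep the 0.05 family-wise error of the flat 0.025 rule and give more power for the second drug; the flat rule is valid, so this is an improvement and not a correction

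*Protocol*

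**What the plan says.** Protocol section 6.3 derives two P-values for the primary outcome, one for each drug against placebo, and sets one criterion for both: "a P-value of 0.025 will be considered significant, applying a Bonferroni correction for multiple comparisons". The reason it gives is the number of primary comparisons.

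Section 6.5 sizes the trial to match. It starts from the two hypotheses ("Since PIVENS is a three group trial with two primary hypotheses") and lists "Two-sided type I error (0.025, Bonferroni corrected for two comparisons") and "Type II error (0.10; i.e., 90% power"). The assumed rates are "expected proportion improved in placebo group (assumed=0.14") and "expected proportion improved in pioglitazone or vitamin E group (0.40"), with "equal allocation to each of the three treatment groups (80 per group").

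Section 6.6 plans one interim analysis of the primary outcome for the DSMB, at about half the data, and says that "O'Brien-Fleming statistical stopping guidelines for efficacy apply". It gives no alpha level and no critical values. Sections 6.3 and 6.5 do not mention the interim.

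**The concern.** The flat rule holds both drugs to 0.025 whatever the other one shows. Suppose one drug is clearly effective and the other has P = 0.04. Section 6.3 calls the second drug negative, while Holm, with the same family-wise protection, calls it positive. The trial asks a separate question about each drug, and section 6.5 concedes that there were no data on the vitamin E response and borrows the pioglitazone rate. Two drugs of unequal strength are therefore a realistic outcome, and a second P between 0.025 and 0.05 is where the choice of rule decides the conclusion.

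A side issue is that 0.025 and the O'Brien-Fleming guideline stand in different sections with no link. If 0.025 is the total alpha per comparison, part of it is spent at the interim, and the final critical value lies slightly below 0.025.

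**Working it through.** **Inputs (section 6.5):** placebo 0.14, active 0.40, two-sided alpha 0.025, power 0.90, 80 per arm, 10% missing. The interim is at information fraction 0.5 (section 6.6). Evaluable patients per arm: 80 × 0.9 = 72.

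**1. The plan's own figure.** Mean rate = (0.14 + 0.40)/2 = 0.27.

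- √(2 × 0.27 × 0.73) = 0.6279
- √(0.14 × 0.86 + 0.40 × 0.60) = 0.6003
- n = (2.2414 × 0.6279 + 1.2816 × 0.6003)² / 0.26² = 2.1766² / 0.0676 = 70.08, rounded up to 71
- 71 / 0.9 = 78.9, that is 79, which the protocol gives as approximately 80

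The stated 71 is reproduced. Power per comparison by the formula at 0.025 is 90.4% with 71 per arm and 93.7% with 80. The flat rule meets its target.

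**2. Why Holm dominates in rejections.** Order the P-values so that P(1) ≤ P(2).

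- Bonferroni rejects each hypothesis with P ≤ 0.025.
- Holm rejects the first if P(1) ≤ 0.025 and then rejects the second if P(2) ≤ 0.05.

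Every Bonferroni rejection is also a Holm rejection. Family-wise error stays at or below 0.05 under any dependence, so the shared placebo arm does no harm.

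**3. Size of the gain.** Simulation of three binomial arms with a shared placebo arm: pooled z-test, 72 per arm, placebo 14%, 1,000,000 trials, one look.

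| Case | Quantity | Flat 0.025 | Holm |
|---|---|---|---|
| Both drugs 40% (protocol) | power per drug | 91.3% | 94.4% |
| Both drugs 40% (protocol) | both shown | 85.2% | 91.3% |
| Both drugs 40% (protocol) | at least one shown | about 97% | same |
| 40% and 35% (my assumption) | weaker drug shown | 76.8% | 84.0% |
| 40% and 30% (my assumption) | weaker drug shown | 53.2% | 64.7% |
| 40% and 14% (null drug) | null drug falsely shown | 2.3% | 4.5% |

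Section 6.4 counts missing patients as unimproved. Taken that way, the rates become 0.9 × 14% = 12.6% and 0.9 × 40% = 36% with 80 per arm. Power to show both then goes from 83.6% to 89.9%. The gain does not depend on how missing biopsies are handled.

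**4. The interim.** For one look at half the information, solve P(|Z₁| > c√2 or |Z₂| > c) = α with correlation √0.5.

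- α = 0.025: c = 2.250. Interim z = 3.183 (P = 0.0015), final P = 0.0244.
- α = 0.05: c = 1.977. Interim z = 2.797 (P = 0.0052), final P = 0.0480.

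Error if the final analysis kept an unadjusted 0.025 (simulated, shared placebo arm, correlation 0.5):

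| Interim boundary | Error per comparison | Family-wise error |
|---|---|---|
| None | 0.025 | 0.046 |
| O'Brien-Fleming at 0.025 | 0.0256 | 0.047 to 0.048 |
| O'Brien-Fleming at 0.05 (assumption) | 0.028 | 0.051 to 0.052 |

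Moving the final level from 0.025 to 0.0244 changes power from 90.4% to 90.2% at 71 per arm and from 93.7% to 93.6% at 80. The required n stays 71.

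**The case against.** The strongest reply is that nothing is wrong. Sections 6.3 and 6.5 agree, the sample size is reproduced, Bonferroni is valid, and each comparison has its 90% power. Holm does not raise the chance of finding at least one effective drug. All of this stands, and it is why the point is an improvement and not an error.

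Bonferroni also has simple simultaneous confidence intervals that match its tests, which Holm lacks. That is a real loss, but a limited one, since section 6.3 promises no such intervals for the primary comparisons.

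The larger gains in the table rest on response rates of 30% and 35% that are not in the protocol. They show a range only. The gain at the protocol's own 40% needs no outside assumption. The simulations use a single look, so they do not give the power of Holm combined with the interim.

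A reader might infer that the protocol tests at 0.025 at the end in spite of the efficacy interim and so inflates type I error. The text does not support this. Section 6.3 explains 0.025 only as the split between two comparisons. Section 6.6 invokes O'Brien-Fleming, which carries its own final boundary, and exact critical values may properly be left to the SAP. Even an unadjusted 0.025 at the end keeps family-wise error below 0.05 if the interim runs at 0.025. An excess appears only if the interim boundary were set at 0.05 per comparison, which the protocol does not say.

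**Conclusion.** The flat 0.025 rule is sound but gives away power for the second drug. Under the section 6.5 rates and 72 evaluable patients per arm, Holm adds about 3 percentage points per drug and about 6 points for showing both, at the same family-wise level of 0.05. If one drug is weaker than planned, the gain for that drug is about 7 points at a 35% response and about 11 points at 30%, both of them my assumptions. The missing link between 0.025 and the O'Brien-Fleming guideline calls for a clarifying sentence and is no evidence of a type I error problem.

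**What to change.** Before unmasking, and before the interim analysis if it is still to come:

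- **Section 6.3.** Replace the flat rule with Holm: the smaller of the two P-values is tested at 0.025 and, if it is rejected, the other is tested at 0.05. Leave the sample size in section 6.5 at 0.025, as a conservative basis.
- **Section 6.6, as a clarification.** State that O'Brien-Fleming applies within each Holm level. For 0.025: interim P ≤ 0.0015, final P ≤ 0.0244. For 0.05: interim P ≤ 0.0052, final P ≤ 0.0480. Recompute these at the actual information fraction. State how the second comparison is tested if the first crosses its boundary at the interim.

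If the sponsor keeps the flat rule, one sentence in section 6.6 is enough: O'Brien-Fleming at 0.025 per comparison, with the final critical value.

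Cost: no extra patients. The first-step final level is 0.0244 instead of 0.025, about 0.1 to 0.2 points of power by the formula above. The simple matching simultaneous intervals are lost. The text is short, but it changes the primary success rule and so needs a protocol amendment with the usual approvals. It has to be fixed in advance, because a move to Holm after the P-values are known would not be credible.

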6.2. Outcome measures

Primary outcome measure:

The primary outcome measure requires improvement in NASH activity after 96 weeks of treatment as determined by liver biopsies pre- and post-treatment. The measure is derived from changes from baseline to the end of treatment in the NASH CRN NAFLD/NASH activity score (NAS). The NAS ranges from 0 to 8 (highest activity) and is calculated as the sum of three components of the standardized histologic feature scoring system for liver biopsies:

NAS	=	Steatosis score $(0-3) +$
		Lobular inflammation score $(0-3) +$
		Hepatocyte ballooning score (0-2)

As noted earlier, a NAS of 5 or greater with each subscore at least 1 or a NAS of 4 with each subscore at least 1 and a finding of definite steatohepatitis by at least two of three NASH CRN pathologists is a requirement for enrollment into the trial.

38

The definition of improvement after treatment as the primary outcome measure requires the following three conditions:

- No worsening of the fibrosis feature score
- Improvement by at least 1 point in the hepatocyte ballooning feature score
 - Either: (1) Improvement in NAS by 2 or more points spread across at least two of the NAS components, OR
 - (2) Post-treatment NAS is 3 points or less

Secondary outcome measures:

- Change in NAS after 96 weeks of treatment compared to baseline NAS. Mean changes in NAS will be compared.
- Changes in fibrosis, steatosis, lobular inflammation, cellular ballooning and other specific features from the histologic scoring system after 96 weeks of treatment compared to baseline. Improvement in specific features will be defined as any improvement in the score. Mean changes will also be compared.
- Change in serum aminotransferase levels after 96 weeks of treatment compared to baseline. A biochemical response is considered a fall of ALT levels into the normal range. Patients are not required to have abnormal levels of aminotransferases in order to enter this trial as long as they meet histological and other clinical criteria. Therefore, patients with normal levels of transaminases may be enrolled. If an adequate number of such patients are enrolled, a subgroup analysis will be performed.
- Change in anthropometric measurements (weight, BMI, waist-to-hip ratio, waist circumference, triceps skin fold thickness and total body fat) after 96 weeks of treatment compared to baseline.

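### The primary test does not use centrally read baseline NAS, on which the responder rule depends, and the only covariate model has no defined trigger, no named covariates and no mention of clinic

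*Protocol*

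**What the plan says.** Section 6.3 derives two primary P-values, one per active arm against placebo, from the Mantel-Haenszel test for stratified 2x2 tables. The stated reason for stratifying is "since the randomization is stratified by clinic". Each P-value is judged at 0.025.

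The section then expects confounding to be unlikely, and provides for it as follows: "if confounding should occur, logistic regression analyses with histologic improvement as the binary response and treatment group indicator and any suspected confounders". The stated purpose is to see how sensitive the primary P-value is to confounding. No criterion for confounding is given, no covariate is named, and clinic is neither listed nor expressly excluded. The same kind of trigger is repeated for the secondary outcomes.

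The outcome being analysed (section 6.2) requires all of the following:
- fibrosis does not worsen;
- ballooning falls by at least one point;
- either "Improvement in NAS by 2 or more points spread across at least two of the NAS components" or a post-treatment NAS of 3 or less.

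Section 5.7 says that baseline and follow-up biopsies are scored centrally and that the central scores are the ones analysed. Baseline NAS is therefore in hand, but section 6.3 does not mention it as a covariate.

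**The concern.** There are two related weaknesses.

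First, the responder rule is written partly in terms of where the patient ends up, so the change required depends on where the patient starts. A baseline value built into the endpoint in this way is the natural adjustment variable. It is collected for the trial's own purposes, and the primary analysis leaves it aside.

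Second, the one place where covariates may appear is tied to what is observed. Under randomization any imbalance is chance. Whether it amounts to confounding, and which variables enter the model, can be settled with outcomes in view. If clinic is left out as the text literally reads, the sensitivity model differs from the primary test in two respects at once: it drops the stratum and adds the covariates. A shift in the P-value could not then be assigned to either.

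At stake are a modest amount of power in the two primary comparisons and the usefulness of the robustness check. The validity of the primary test is not at stake.

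**Working it through.** **1. The plan's own figure.** Section 6.5 gives "Two-sided type I error (0.025, Bonferroni corrected for two comparisons"), "Type II error (0.10; i.e., 90% power"), "expected proportion improved in placebo group (assumed=0.14") and "expected proportion improved in pioglitazone or vitamin E group (0.40"). The mean proportion is (0.14 + 0.40)/2 = 0.27.

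n = [2.2414 × √(2 × 0.27 × 0.73) + 1.2816 × √(0.14 × 0.86 + 0.40 × 0.60)]² / 0.26²
= [2.2414 × 0.6279 + 1.2816 × 0.6003]² / 0.0676 = 70.1, rounded up to 71.

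71/0.90 = 78.9, so 79, which the protocol states as about 80. The figure reproduces. Power is 90.4% at 71 per group and 93.7% at 80.

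**2. What the responder rule asks, by central baseline score.** This assumes that no other component rises and fibrosis does not worsen.

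| Baseline | Smallest qualifying change |
|---|---|
| Ballooning 0 | None: the required ballooning fall is impossible |
| NAS 4, ballooning 1 or 2 | One point of ballooning (4 − 1 = 3) |
| NAS 5 | Two points (5 − 1 = 4 is too high); ballooning 2 to 0 alone suffices (5 − 2 = 3) |
| NAS 6 to 8 | Two points across at least two components; ballooning alone falls by at most 2, and 6 − 2 = 4 is too high |

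Eligibility rests on the local reading and analysis on the central one, so a central NAS below 4, or central ballooning of 0, can occur. A high baseline also leaves more room to fall, which works in the opposite direction.

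**3. What the rule alone implies.** Assume equal, independent chances of a one-point fall in each component, calibrated to 14% and 40% overall. Placebo response is then 24% at NAS 4 against 11% at NAS 5 to 8, and active response 49% against 37%. With score rises and fibrosis worsening added, the figures are 21% against 11–12%, and 46% against 37–42%. The NAS distribution and movement probabilities are assumptions. In this setting, adjusting for NAS 4 against 5 or more gained 0 to 1 point of power.

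**4. Power with a stated prognostic strength.** The documents give neither the NAS distribution nor its odds ratio (OR) per point, so both are assumed. All runs use 8 clinics and alpha 0.025; MH is the clinic-stratified Mantel-Haenszel test.

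(a) 72 evaluable per arm (0.90 × 80), 14% against 40%, clinic-stratified score test adjusted for NAS. MH power is 91–92%. Adjusted power is 91.2% at OR 1.0, 92.9% at 0.61 and 94.3% at 0.45. Type I error is 0.021–0.026. At 14% against 32%, power moves from 63.5% to 66.2% and from 64.3% to 69.2% at the latter two ORs.

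(b) 80 per arm with 10% missing counted as unimproved, as section 6.4 states: 0.90 × 0.14 = 12.6% and 0.90 × 0.40 = 36%.

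| OR per point | MH | NAS-adjusted | Difference |
|---|---|---|---|
| 1.0 | 90.6% | 91.5% | 0.9 |
| 0.61 | 89.7% | 92.5% | 2.8 |
| 0.45 | 91.0% | 93.8% | 2.8 |

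An unconditional logistic score test with clinic indicators rejected 3.2–3.6% of the time at nominal 2.5%. At OR 1.0 there is nothing to gain, so the 0.9 there should not be credited to adjustment.

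(c) 80 per arm, 14% against 40%, opposite direction, ordinary logistic model with NAS.

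| OR per point | MH | NAS-adjusted | Difference |
|---|---|---|---|
| 1.0 | 93.5% | 93.9% | 0.4 |
| 1.35 | 93.5% | 94.4% | 0.9 |
| 2.0 | 94.1% | 96.6% | 2.5 |
| 3.3 | 94.2% | 98.8% | 4.6 |

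The last row implies an odds ratio of 3.3⁴ ≈ 119 between NAS 4 and NAS 8, so it is an extreme case.

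**5. Does the conditional trigger damage the error rate?** With adjustment used only when baseline NAS was imbalanced at P < 0.10, type I error was 0.020–0.026 at nominal 0.025. If the smaller of the two P-values were reported, it would be 0.027–0.037 for ORs of 1.0 to 2.0 and up to 0.048 at 3.3.

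**The case against.** The strongest reply is that the primary analysis has no error to correct. The Mantel-Haenszel test is fixed in advance, valid, and matched to the randomization. The logistic model is labelled a sensitivity analysis, and its details may stand in a statistical analysis plan that is not at hand. Choosing an adjusted test instead is a matter of efficiency, and its benefit rests on assumed inputs. Even the direction of the NAS effect is unsettled, so a linear term might gain little.

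Most of this stands, and it limits the point. It does not remove it. The protocol does more than leave detail open: it makes adjustment depend on what is observed, and an analysis plan that followed it would inherit that rule. The uncertain direction argues for NAS in categories and does not argue for ignoring it.

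Three stronger readings are tempting and are not supported:
- A reader might infer that covariates picked after the fact can enter the primary comparison. No text lets the logistic result replace the Mantel-Haenszel result, so the inflation from taking the smaller P-value describes something the protocol does not permit.
- A reader might infer that chance imbalance would nearly always fire the trigger. The protocol contains no rule for screening baseline variables, and it speaks of covariates related to the change in histologic score, which is more than imbalance.
- A reader might infer that adjustment can only help. Without prognostic value there is nothing to gain, and the effect measure becomes a conditional odds ratio.

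**Conclusion.** The point holds as an inexpensive improvement. The primary test is valid and prespecified but ignores a collected baseline value that the responder definition itself depends on. The only covariate model has an undefined trigger, an open covariate list and no stated place for clinic.

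The expected gain is about 0 to 3 points of power at the planned effect. It lies near the bottom of that range if the link between baseline NAS and response comes from the rule alone, and near the top at odds ratios of about 0.45 to 0.61, or 2.0, per NAS point. Larger gains appeared only under an extreme odds ratio or a smaller treatment effect. If NAS is not prognostic, no material loss is expected. All of this rests on assumed NAS distributions and prognostic strengths. The sample size is unaffected.

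**What to change.** In section 6.3, replace the confounding trigger with one prespecified analysis per primary comparison, run whatever the observed balance:
- a clinic-stratified test adjusted for centrally read baseline NAS, for example a conditional logistic score test stratified by clinic;
- NAS in categories, such as 4 or less against 5 or more, because the relation may not be linear;
- the conditional form in preference to clinic indicators in an ordinary logistic model, which was slightly liberal in the check above.

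State in advance which test decides at 0.025. Preferably this is the adjusted test, with the unadjusted Mantel-Haenszel test in support; at minimum, the reverse. Keep clinic in every model and report a standardized risk difference with its interval. Treat the parallel trigger for secondary outcomes in the same way.

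The cost is wording and a little programming. No new data or patients are needed. The one drawback is that the conditional odds ratio has to be read beside the risk difference.
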